3.1 Description of Study Design

We will use a prospective, RCT study design to compare primary and secondary outcomes of the CATCH group (n = 15) with a control group (n = 7). This study uses a RCT design to control for confounders, to minimize imbalances in characteristics between the groups at baseline, and to demonstrate feasibility of carrying out a RCT research protocol in preparation for a larger study.^{75,76}

Random allocations to treatment group will be concealed to avoid bias.⁷⁵ The clinician who will administer the exercise stress tests pre- and post-treatment will be blinded to the treatment group assignment. We will also use a qualitative (descriptive, exploratory) study design to evaluate patient acceptability of CATCH and analyze themes of 15 semi-structured interviews.

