A rapid, upper thoracic breathing pattern allows insufficient time to empty the lungs;^{24,29,30} it increases the work of breathing and dyspnea, and contributes to retention of CO₂.⁸ Rapid breathing and hyperinflation can worsen airway secretions and bronchoconstriction⁸ and cause the loss of elastic recoil.²⁴ Rapid breathing due to exercise intolerance and emotional stress can lead to neuromechanical uncoupling (failure of the ventilatory pump and CO₂ retention)^{29,31} and associated panic, fear, and emergency medical care.²⁹

Altered breathing behavior also leads to neuroplasticity and a profound network disorganization between the sensorimotor cortex and brainstem in COPD.¹⁵ Sensory neural coding of breathing patterns (muscle mechanics, CO₂, pressure, volume, and airflow) are gated into the cerebral cortex for conscious cognitive and emotional processing based on individual threshold levels.³²

Benefits of Breathing Training

Slow breathing training is an important rehabilitation and self-management intervention to systematically alleviate dyspnea, prevent or manage dyspnea crisis³³, manage anxiety and panic in COPD,³⁴⁻³⁶ and improve sympathovagal imbalance⁹. Breathing techniques designed to mitigate the ventilatory consequences of COPD include pursed lips breathing (PLB), pranayama yoga breathing, diaphragmatic breathing (DB), Buteyko breathing technique,³⁷⁻³⁹ mindful breathing⁴⁰⁻⁴², and device-guided breathing with biofeedback. Given that respiratory muscles are under both brainstem and skeletal muscle control, patients can learn to control their respiratory rate (RR) to help manage their symptoms.^{8,9,39,43} In a systematic review of sixteen breathing studies of breathing exercises of four to 15 weeks for COPD, the breathing exercises were found to improve exercise capacity compared to no intervention.⁴⁴

However, the effects of breathing training on dyspnea and functional status for COPD have been equivocal, possibly hampered by the wide variation of breathing exercises and protocols studied.^{45,46} Therefore, more evidence of the effectiveness of breathing training is needed to guide clinical practice.^{10,11,47} The quality of most studies of breathing exercises were reduced by the lack of assessor blinding.⁴⁴

Study Importance and Innovation

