The rationale supporting the importance and innovation of this trial study is that: (1) it uses a novel therapeutic approach; both a novel capnometer computer system and a newly developed smartphone breathing app (new to both pulmonary rehabilitation and COPD) to promote improved learning and adherence to home breathing exercises; (2) it includes anxiety and physiological outcomes omitted from

CONFIDENTIAL

This material is the property of the NYU School of Medicine and Langone Medical Center. Do not disclose or use except as authorized in writing by the study sponsor Behavioral Intervention Template Version: 5 MAY 2017

most previous COPD clinical trials of breathing training to help explain the mechanisms of treatment effects; (3) it includes allocation concealment and assessor blinding of exercise stress testing to address limitations of previous studies; and (4) it includes an expanded theoretical base of breathing training effects to potentially improve dyspnea management outcomes. This breathing study is important because it measures physiological, performance-based, and patient-reported outcomes (including anxiety) to more comprehensively study the benefits of breathing training in COPD.

The proposed study translates new theory from basic science and brain imaging studies to promote improved dyspnea management for COPD. The novel breathing training protocol is designed to both modulate perception of dyspnea at the CNS level as well as improve neuromechanical coupling (matching between respiratory effort and the mechanical response of the respiratory system). Breathing training is theorized to improve neural connections, that is, decrease activity of the amygdala in the limbic system and improve prefrontal cortical regulation, as well as decrease arousal of the sympathetic nervous system.^{15,32,41,48,49}

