1.2 Rationale

Hypotheses

1. Participants' change scores in the CATCH group will be significantly greater compared with those of the control group for the primary outcomes of peak HR, exercise duration, 6MWD, DMQ-CAT dyspnea, SGRQ quality of life, and exercise adherence (> % of sessions or < time to complete).
2. Ve will decrease (indicating decreased RR and improved breathing efficiency) and peak VO₂ will increase in the CATCH group (indicating improved pulmonary function) and changes will be significantly greater compared with the control group.
3. Participants' change scores in the CATCH group will be significantly greater compared with the control group for the secondary outcomes of RR, ETCO₂, Borg RPE, anxiety, CRQMaster, SEBQ, PROMIS-36, and Physical Activity.

CONFIDENTIAL

This material is the property of the NYU School of Medicine and Langone Medical Center. Do not disclose or use except as authorized in writing by the study sponsor Behavioral Intervention Template Version: 5 MAY 2017

Justification for hypotheses

Our hypotheses for the primary outcomes of Ve, peak VO₂, and exercise time are consistent with findings and trends from a previous COPD trial of device-guided respiratory training combined with PR.⁴³ By allowing more time to effectively empty the lungs during prolonged exhalation, a slow breathing pattern can improve breathing efficiency, reduce lung hyperinflation, improve diaphragmatic mobility and chest wall mechanics, resulting in less dyspnea, improved exercise capacity and tolerance, eucapnia (optimal carbon dioxide pressure), and the prevention of neuromechanical uncoupling.^{8,59,24,29} In a meta-analysis of four studies of mostly severe COPD, slow breathing exercises (PLB, DB, and 3-months of yoga) improved 6MWD by 35 - 50 meters, which was beyond the minimal important difference^{47,44}.

Device-guided slow breathing training when combined with PR using a pneumotachometer interfaced with a computer display of respiratory and goal feedback reduced dynamic hyperinflation and improved breathing pattern (increased expiratory time) in COPD compared with both PR-alone and breathing-training-alone groups.⁴³ Device-guided breathing instruction in COPD also improved self-efficacy (breathing confidence) compared with a traditional method of teaching pursed lips breathing (PLB).⁶⁰

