Some breathing exercises during CATCH sessions will be audio or video recorded or photographed to provide participants with additional instructions to use at home to help them complete guided home breathing exercises. For the at-home training, patients will also use the Address Stress app on a smartphone or computer tablet for tailored paced breathing exercises. The breathing app will provide auditory and visual cues for the paced exercises. Patients will also keep a breathing exercise log of total

CONFIDENTIAL

This material is the property of the NYU School of Medicine and Langone Medical Center. Do not disclose or use except as authorized in writing by the study sponsor Behavioral Intervention Template Version: 5 MAY 2017

daily minutes completed. Patients will also be instructed in upper body stretching exercises to perform daily as part of their home exercises.⁸⁶ The Address Stress app collects email address for downloading the app on a personal smartphone or tablet computer. The app transmits adherence data only via email to the study PI. It is not necessary for participants to own a smartphone or tablet computer to use the app since tablet computers will be loaned to participants as needed to access the app.

CATCH will be grounded in social cognitive theory⁸⁷ to promote behavior change, improve selfefficacy and outcome expectation, and support the use of interactive technologies to guide and motivate patients. CATCH also applies the hyperventilation model, in which hyperventilation leads to hypocapnia, dyspnea, and panic.⁸⁸ Other underlying theoretical models are the neurophysiological model of dyspnea,³¹ the model of mindfulness⁴⁸, and the neurophysiological theory of functional connectivity in COPD.¹⁵

Pulmonary Rehabilitation (PR).

Patients in both treatment groups will participate in a 10-week (16 - 20 sessions) comprehensive PR program. As per standard of care, the control group will receive the 10-week PR program with traditional breathing training instruction only (without biofeedback). The PR program comprises two or three exercise training sessions per week implemented by physical therapists (each of 1-hour duration). PR sessions include individualized self-management education.

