6.1.1 Study Specific Procedures

See Schedule of Events – Attachment A for description of study specific procedures.

Figure 2. CATCH Scheduling of Tests.

CONFIDENTIAL

This material is the property of the NYU School of Medicine and Langone Medical Center. Do not disclose or use except as authorized in writing by the study sponsor Behavioral Intervention Template Version: 5 MAY 2017

Outcome Measures.

Exercise Capacity: Clinical treadmill stress tests will be used to measure exercise capacity pre- and post-treatment, including: peak VO_2 (ml/kg/min and % predicted based on age), Ve (l/min) at isotime (2-minutes prior to exercise termination at baseline), peak HR, and exercise duration. Exercise stress tests will be administered by a clinician as part of standard care.

Six Minute Walk Test (6MWT). The 6MWT is a standardized, performance-based test to measure exercise tolerance (functional status) using the American Thoracic Society's standardized protocol.⁸⁹ Clinicians will administer the 6MWTs as part of standard care.

Dyspnea Management Questionnaire Computer Adaptive Test (DMQ-CAT)⁹⁰. The DMQ-CAT is a COPD-specific functional status measure that captures four dyspnea domains: intensity, anxiety, activity avoidance, and self-efficacy. Higher scores are better. It has been shown to be reliable and valid in rehabilitation and primary care patients.^{91,92} The DMQ-CAT uses computer adaptive testing to tailor dyspnea items and administer up to 20 items.

St. George's Respiratory Questionnaire (SGRQ).^{93,94} The SGRQ is a widely used quality of life measure for adults with chronic airflow limitation, consisting of three domains: symptoms, activity, and impacts. Lower scores indicate better quality of life. The SGRQ activity domain measures dyspnea and its functional impact. The symptoms and impacts domains measure several respiratory symptoms and psychosocial functioning respectively. Several studies have supported its reliability and validity.^{93,95,96} We will use the American version for this study.⁹⁴

Adherence to Exercise Training. Exercise adherence is the % of exercise training sessions completed and the time taken (in weeks) to complete the PR program. Adherence to daily home breathing exercises is the % completed (at least 5 minutes per day for 6 weeks; the goal is 70% adherence).

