Respiratory rate (RR) (breaths/minute) and **End-Tidal Carbon Dioxide Tension (ETCO₂)** in mmHg). Resting RR and ETCO₂ will be measured during 5 minutes of quiet sitting without providing any feedback using capnometry. Nasal cannula and a sampling tube are attached to the capnometer monitor to measure post-exhaled air. Average RR and ETCO₂ values will be calculated.

Generalized Anxiety Disorder Scale (GAD-7).⁹⁷ The GAD-7 will be used to measure anxiety. A cut point of five or greater will be used to detect anxiety.⁹⁸

CONFIDENTIAL

This material is the property of the NYU School of Medicine and Langone Medical Center. Do not disclose or use except as authorized in writing by the study sponsor Behavioral Intervention Template Version: 5 MAY 2017

Borg Rating of Perceived Exertion (RPE) Scale.⁹⁹ The Borg RPE scale is a 15-grade, single-item rating scale, ranging in score between 6 and 20. Clinicians will administer the Borg RPE Scale with the 6MWT as part of routine pre-treatment and post-treatment evaluations.

Chronic Respiratory Questionnaire-Mastery (CRQ-Mastery).^{100,101} The CRQ-Mastery is an obstructive lung disease-specific quality of life measure that includes four items to measure patients feeling of control over their disease. The reliability and validity of the CRQ is well established.^{95,102}

Self-Evaluation of Breathing Questionnaire (SEBQ).¹⁰³ The SEBQ is a 12-item measure of dysfunctional breathing symptoms with two domains: i) lack of air (sensations of air hunger); and ii) perception of inappropriate or restricted breathing (related to work of breathing and biomechanics of breathing).

Patient-Reported Outcomes Measurement Information System (PROMIS-36).^{104,105} To measure generic QOL we will implement PROMIS-36 Short Forms to measure six domains: physical function, anxiety, depression, sleep disturbance, fatigue, and satisfaction with participation in social roles. Higher scores will indicate more of the concept being measured.¹⁰⁴ Raw scores will be transformed into item response theory calibrations with a mean score of 50 and a SD ± 10 .

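### Assessor blinding is planned only for the treadmill stress test; the 6MWT and the Borg RPE taken with it have no planned masking, which leaves an avoidable risk of assessor bias in 6MWD, a Hypothesis 1 outcome

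*Combined protocol and SAP*

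**What the plan says.** Section 1.1 says of the earlier literature: "The quality of most studies of breathing exercises were reduced by the lack of assessor blinding". Under its heading on importance and innovation, the same section says of this trial that "it includes allocation concealment and assessor blinding of exercise stress testing to address limitations of previous studies". Section 3.1 puts this into the design: "The clinician who will administer the exercise stress tests pre- and post-treatment will be blinded to the treatment group assignment".

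Section 6.1.1 describes the outcome measures one by one. On exercise capacity it says: "Clinical treadmill stress tests will be used to measure exercise capacity pre- and post-treatment". The walk test has its own entry, with a standardised published protocol, and there the plan says: "Clinicians will administer the 6MWTs as part of standard care". On exertion it says: "Clinicians will administer the Borg RPE Scale with the 6MWT as part of routine pre-treatment and post-treatment evaluations". Section 6.1.2 and Attachment A list cardiopulmonary exercise testing and the 6MWT as separate standard-of-care procedures and say nothing on masking.

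On status, Hypothesis 1 in section 1.2 expects larger changes with CATCH "for the primary outcomes of peak HR, exercise duration, 6MWD, DMQ-CAT dyspnea, SGRQ quality of life, and exercise adherence". Borg RPE comes under Hypothesis 3. Sections 3.2.1 and 3.2.2 make feasibility and acceptability the primary endpoints, with 6MWD and Borg RPE secondary.

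**The concern.** The protocol counts absent assessor blinding as a quality problem in this field and offers its own blinding as a remedy. The remedy reaches one of the two exercise tests. The other, the 6MWT, depends on the participant's effort, and a tester who knows the arm can influence that effort through instructions and encouragement. Arm knowledge can matter most at Week 10, when CATCH participants have had their six sessions.

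There are plausible routes for such knowledge to reach testers. The trial has a single site, both arms attend the same PR programme for 16 to 20 sessions, and CATCH runs alongside it in about Weeks 0 to 6. Participants know whether they received capnometry sessions.

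What is at stake is how the 6MWD contrast can be read. Objective 1 in section 2.1 rests feasibility partly on estimates of short-term treatment effect, section 3.1 says the trial prepares for a larger one, and section 8 compares the arms on these outcomes at the 0.05 level. A tester effect in 6MWD would carry into those estimates.

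**Working it through.** The point is about scope, so the main check is to set the sections side by side.

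| Measure | Who administers it | Masking planned |
|---|---|---|
| Treadmill stress test (peak VO2, Ve, peak HR, duration) | A clinician, in standard care (6.1.1) | Yes (1.1, 3.1) |
| 6MWT distance | Standard-care clinicians (6.1.1, 6.1.2) | None stated |
| Borg RPE | Clinicians, with the 6MWT (6.1.1) | None stated |

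1. Could the blinding sentence in 3.1 cover the walk test? No. Section 6.1.1 identifies the stress test as a treadmill test and treats the 6MWT under a separate heading. Attachment A also lists the two on separate lines.
2. Does delivery in standard care rule masking out? No. The treadmill test is also a standard-care procedure, and its clinician is to be blinded.
3. Would masking help both measures equally? No. 6MWD is measured by the tester. Borg RPE is a rating by a participant who knows the arm, so a masked tester removes only the tester's own influence.

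**Size.** The documents give no figure for a tester effect. The only design figure is in section 8: about 80% power for a difference of 1.25 SD with 22 patients randomised 2:1, two-sided 0.05. It reproduces by the normal approximation with arms of 22 × 2/3 = 14.67 and 22/3 = 7.33:

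- SE = √(1/14.67 + 1/7.33) = 0.452 SD
- 1.25/0.452 − 1.96 = 0.80, so power = 78.9%

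With arms of 15 and 7 and the t distribution on 20 df, it is 73.8%. The present point does not depend on this figure.

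To show what a tester effect could do at this sample size, assume no true effect and a shift of b SD in favour of CATCH that comes from the tester alone. For an unadjusted two-sided 5% t test with arms of 15 and 7, the noncentrality is b × √(15 × 7/22) = 2.185b on 20 df:

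| Assumed shift b (SD) | Rejection rate with no true effect |
|---|---|
| 0 | 5.0% |
| 0.1 | 5.5% |
| 0.2 | 7.0% |
| 0.3 | 9.6% |
| 0.5 | 18.0% |

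Every value of b is an assumption. The table shows sensitivity and does not estimate the bias in this trial.

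**The case against.** The strongest reply is that the plan is silent on these testers and does not say that they know the arm. Section 10 promises a data collection manual, which might address masking, and the scheduling figure might add detail. Section 1.1 limits its blinding claim to stress testing, so nothing is misdescribed. The 6MWT follows a standardised protocol and is done by trained clinicians. CATCH is delivered by the principal investigator, an occupational therapist, and PR by physical therapists, so delivery is already partly separate. The primary endpoints do not depend on who runs the walk test, and section 8 calls the between-group analyses preliminary.

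Most of this stands, and it limits the point. The finding is a missing safeguard, and standardisation is a real protection. Standardisation is still not masking, however, and a manual yet to be written cannot be credited with a rule that the protocol does not state. The secondary status of 6MWD lowers the stakes without removing them, because Objective 1 uses the effect estimates.

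A reader might infer more than the documents support:

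- That the protocol calls missing blinding the main weakness of earlier studies. It says that this reduced the quality of most of them, and it suggests varied exercises and protocols as a possible reason for the equivocal effects.
- That a masked tester is the only protection. The standardised protocol is another.
- That PR therapists progress exercise differently by arm. The plan says of delivery that "The PR program comprises two or three exercise training sessions per week implemented by physical therapists", for both arms; nothing shows progression that depends on the arm.
- That the bias can be expressed as a share of the 35 to 50 m benefit cited in section 1.2. No tester effect is documented. The benchmark also comes from other slow-breathing regimens, whereas the controls here receive PR with traditional breathing instruction.

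**Conclusion.** The point holds as a gap in the plan. Assessor blinding is limited to the treadmill test, and the 6MWT and Borg RPE are left to standard-care clinicians with no planned masking. This leaves an unmitigated risk of assessor bias in 6MWD, a Hypothesis 1 outcome that is formally secondary and contributes to the Objective 1 effect estimates. For Borg RPE, a Hypothesis 3 self-rating, masking would help only in part.

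The documents neither demonstrate a bias nor allow its size to be derived; the 5.5% to 18.0% range rests wholly on assumed shifts of 0.1 to 0.5 SD. The conclusion assumes that protocol silence means no masking procedure is planned, and that 6MWD can respond to tester behaviour even under a standardised protocol. The change is worth making because it is cheap and meets a standard the protocol itself invokes.

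**What to change.** In sections 3.1 and 6.1.1, extend the existing blinding to the walk test:

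- Have the Week 0 and Week 10 6MWT and Borg RPE run by the clinician already masked for the stress test, or by an existing PR clinician who did not treat that participant and does not know the arm.
- Use one fixed wording for encouragement within the standardised protocol already cited, and ask participants not to disclose their arm before testing.
- Record the tester's masking status for every test. Where masking was not achieved, report the result as an unmasked assessment.
- Unless the 6MWT masking is achieved, keep the blinding claim in section 1.1 to the treadmill test.

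The change concerns testers only and does not require withholding CATCH information from treating therapists. It costs protocol wording and a rota rule at one site, with no extra test for participants. Scheduling becomes slightly less flexible, and some participants will still reveal their arm. The documents do not describe staffing, so the site should confirm that an eligible tester is available; recording masking status covers the cases where none is.

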CART	Capnometry-Assisted Respiratory Therapy
CATCH	Capnometry-Assisted Training for COPD to slow the Breath
CFR	Code of Federal Regulations
COPD	Chronic Obstructive Pulmonary Disease
CPET	Cardiopulmonary Exercise Testing
CRF	Case Report Form
CRQ	Chronic Respiratory Disease Questionnaire
DHHS	Department of Health and Human Services
EHR	Electronic Health Record
ETCO ₂	End-tidal Carbon Dioxide
FFR	Federal Financial Report
FWA	Federal-wide Assurance
GCP	Good Clinical Practice
HIPAA	Health Insurance Portability and Accountability Act
ICF	Informed Consent Form
IRB	Institutional Review Board
MBT	Mindful-Based Therapy
MOP	Manual of Procedures
MVPA	Moderate or Vigorous Physical Activity (MVPA)
N	Number (typically refers to participants)
NIDILRR	National Institute on Disability, Independent Living, and Rehabilitation Research
OHRP	Office for Human Research Protections
OHSR	Office of Human Subjects Research
PD	Panic Disorder
PHI	Protected Health Information
PI	Principal Investigator
PLB	Pursed-lips Breathing
PR	Pulmonary Rehabilitation

CONFIDENTIAL

This material is the property of the NYU School of Medicine and Langone Medical Center. Do not disclose or use except as authorized in writing by the study sponsor Behavioral Intervention Template Version: 5 MAY 2017

QA Quality Assurance

QC Quality Control

RR Respiratory Rate

SAE Serious Adverse Event/Serious Adverse Experience

SEBQ Self-Evaluation of Breathing Questionnaire (SEBQ)

SF Short Form

SGRQ St. George's Respiratory Questionnaire

SOP Standard Operating Procedure

US United States

CONFIDENTIAL

This material is the property of the NYU School of Medicine and Langone Medical Center. Do not disclose or use except as authorized in writing by the study sponsor Behavioral Intervention Template Version: 5 MAY 2017

Protocol Summary

Title	CAPNOMETRY-ASSISTED TRAINING FOR COPD TO SLOW THE BREATH (CATCH) TRIAL
Phase	Phase 2.
Methodology	Randomized controlled trial study.
Study Duration	10 weeks.
Duration of behavioral intervention	10 weeks.
Population	Adults with chronic obstructive pulmonary disease (COPD) over 40 years of age; medically cleared to participate in Rusk Rehabilitation's pulmonary rehabilitation program; English speaking.
Study Sites	Rusk Rehabilitation (ACC-16).
Number of participants	40 participants are expected to be enrolled to produce 26 evaluable participants at 1 site.

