2.1 Primary Objectives

Objective 1: Test the feasibility of implementing an RCT of capnometry-assisted training in COPD to slow the breath (CATCH) intervention combined with pulmonary rehabilitation (PR) based on retention of participants with COPD and estimates of short-term treatment effects (at 10 weeks).

Objective 2: Evaluate the acceptability of the CATCH intervention as perceived by participants based on qualitative interviews, CATCH attendance, and adherence to home breathing exercises.

CONFIDENTIAL

This material is the property of the NYU School of Medicine and Langone Medical Center. Do not disclose or use except as authorized in writing by the study sponsor Behavioral Intervention Template Version: 5 MAY 2017

2a. Modify the CATCH intervention based on feedback from participants.

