2.2 Secondary Objectives

1a. Compare a CATCH intervention group (CATCH + PR, n = 15) with a control group (PR alone, n = 7) on the *outcomes* of exercise capacity [peak heart rate (HR), exercise duration, ventilation (Ve), and peak oxygen consumption (VO₂)]; DMQ-CAT dyspnea; 6-minute walk test distance (6MWD); COPD-specific quality of life (St. George's Respiratory Questionnaire); and exercise adherence.

1b. Compare score differences of a 6-week CATCH intervention combined with PR (CATCH + PR, n = 15) with those of a control group (PR alone, n = 7) on the *outcomes* of ETCO₂, RR, Borg Rate of Perceived Exertion (RPE), anxiety, CRQ Mastery, SEBQ, physical activity (PA), and PROMIS-36 quality of life (physical function, anxiety, depression, satisfaction with participation in social roles, sleep disturbance, and fatigue); N = 22.

3 Study Design and Endpoints

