4.6 Total Number of Participants and Sites

Recruitment will end when approximately 40 participants are enrolled at Rusk Rehabilitation for this single-site study. It is expected that approximately 40 participants will be enrolled to produce 22 evaluable participants due to drop-outs.

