Attachment A
Schedule of Events

Activity	EHR PreScreening	Pre- Screening Call	Baseline (Week 0)	Treatment Visits (Weeks 0 – 6 ±2)	Post- Treatment Phone Interview (Week 7 ±2)	PR Discharge Evaluation (Week 10 ±2)
Study team procedures						
Informed Consent		X	X			
Screening						
Age	X		X			
Mini Mental State Examination (MMSE)			X			
Pulmonary Rehabilitation Clearance	X		X			
English Proficiency		X	X			
Pulmonary Function Testing or Chest CT results	X		X			
Medical History (active treatment for lung cancer, supplemental oxygen prescription, cognitive impairment or dementia, unstable cardiac disease / myocardial infarction < 3 months)	X		X			
Body Mass Index	X		X			
Current Smoking Status	X	X	X			
Baseline Assessment						
Modified Medical Research Council Questionnaire (mMRC) ¹⁰⁹			X			
Demographics / Social Economic Status			X			
Lung Function			X			

Smoking History			X			
Pulmonary Diagnoses and Comorbidities			X			
COPD Exacerbation History			X			
Primary Outcome: Feasibility						
Retention of participants: # of drop-outs and # of participants lost to follow-up						X
Primary Outcome: Acceptability (CATCH participants only)						
Semi-structured interviews					X	
% of CATCH intervention sessions attended				X		
Adherence to Breathing Home Exercises – Daily Breathing Log and Address Stress app				X		

CONFIDENTIAL

This material is the property of the NYU School of Medicine and Langone Medical Center. Do not disclose or use except as authorized in writing by the study sponsor
 Drug/Device Template Version: 13 JUN 2016

Study number: s17-01672

Page 2

Version: 6/9/2018

Activity	EHR PreScreening	Pre-Screening Call	Baseline (Week 0)	Treatment Visits (Weeks 0 – 6 ±2)	Post-Treatment Phone Interview (Week 7 ±2)	PR Discharge Evaluation (Week 10 ±2)
Secondary Outcomes						
Cardiopulmonary Exercise Stress Test (CPET) – standard of care			X			X
6-Minute Walk Test & Borg RPE – standard of care			X			X
DMQ-CAT			X			X
St. George's Respiratory Questionnaire			X			X
Generalized Anxiety Disorder (GAD-7)			X			X
End-tidal Carbon Dioxide (ETCO2)			X			X

Respiratory Rate (RR)			X			X
CRQ-Mastery			X			X
Self-Evaluation of Breathing Questionnaire (SEBQ)			X			X
PROMIS-36 SF			X			X
Physical Activity (MVPA)			X			X
Adherence to Pulmonary Rehabilitation Exercise Training Sessions						X
Health Questionnaire						X

CONFIDENTIAL

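### Nothing in the plan ensures that participants who stop CATCH are interviewed, so the primary acceptability endpoint may lean towards those who stayed

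*Combined protocol and SAP*

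**What the plan says.** Section 3.2.1 makes acceptability a primary endpoint, built from qualitative data, the CATCH attendance rate and percentage adherence to home breathing exercises. Retention is the other primary endpoint. Objective 2a in Section 2.1 is to "Modify the CATCH intervention based on feedback from participants".

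Section 3.1 gives the CATCH group as 15 and the control group as 7, and plans to "analyze themes of 15 semi-structured interviews". Attachment A assigns acceptability to CATCH participants only. Its single interview is a phone call after treatment, at Week 7 ±2. Its retention row lists counts of drop-outs and of participants lost to follow-up.

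Section 4.7.1 allows withdrawal at any time and lists grounds for termination, but describes no exit contact. Section 6.1.1 sets a 70% goal for home practice over 6 weeks without saying over whom it is calculated. Section 8 names no analysis population for attendance or adherence.

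On numbers, Section 4.6 says "approximately 40 participants will be enrolled to produce 22 evaluable participants due to drop-outs", while the Protocol Summary says "40 participants are expected to be enrolled to produce 26 evaluable participants at 1 site".

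**The concern.** In an acceptability study, the people who stop are a main source of evidence about what is wrong with the intervention. The protocol's own background takes this view: Section 1.1 cites a trial of mindfulness-based breathing therapy in COPD whose low acceptability was inferred from its retention. Yet this plan fixes the interviews at the number expected to be evaluable in CATCH, times them after treatment, and schedules nothing for someone who leaves earlier.

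If the plan is followed as written, the themes could come mainly from people who stayed, and the changes under Objective 2a would then be shaped by them. A count of drop-outs shows how many left. It does not show why, or what to change. The open denominator for attendance and home practice creates the same exposure: both look better if summarised over those who remained.

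**Working it through.** Inputs: 15 interviews (Section 3.1); groups of 15 and 7 (Sections 2.2 and 3.1); 40 enrolled with 22 evaluable (Section 4.6) or 26 evaluable (Protocol Summary); 2:1 allocation (Section 8); 6 CATCH sessions (Section 5.1); 6 weeks of daily home practice with a 70% goal (Section 6.1.1).

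1. **The plan's own figures.** CATCH share of 22 at 2:1: 22 × 2/3 = 14.7, so 15, leaving 7 controls. Implied loss: 1 − 22/40 = 45%. Both agree with the plan, so 15 interviews equals the evaluable CATCH group under Section 4.6.

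2. **Not interviewed, if all 40 are randomised.** CATCH: 40 × 2/3 = 26.7, about 27. Not interviewed: 26.7 − 15 = 11.7, about 12, or 12/27 = 44%. This gap does not depend on the evaluable number.

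3. **Expected CATCH leavers, assuming also equal loss by arm.**
   - 22 evaluable: 26.7 × 45% = 12.0.
   - 26 evaluable: loss 1 − 26/40 = 35%, and 26.7 × 35% = 9.3. The evaluable CATCH group is then 26 × 2/3 = 17.3, which no longer equals 15.

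4. **If losses come before randomisation.** At the extreme, only 22 are randomised, CATCH has 22 × 2/3 = 14.7, and 15 interviews cover the whole arm. The uninterviewed number therefore runs from 0 to about 12.

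5. **How much the denominator can matter (illustration, assumed values).** Take 27 in CATCH, 15 stayers attending 6 of 6 sessions and 12 leavers attending k. Mean attendance over all 27 is (15 × 6 + 12 × k)/(27 × 6).
   - k = 0: 90/162 = 56%.
   - k = 2: 114/162 = 70%.
   - k = 4: 138/162 = 85%.

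   Over the stayers alone it is 100%. For home practice, if stayers complete 80% and leavers 30%, adherence over all 27 is (15 × 80% + 12 × 30%)/27 = 58%, against 80% in stayers. The two results fall on opposite sides of the 70% goal.

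**The case against.** A reader might infer that leavers are excluded from the interviews and that acceptability is therefore overstated. The documents do not support either statement. Attachment A says only that interviews are for CATCH participants, and nothing limits them to completers. The inference rests on the matching count of 15, the post-treatment timing and the absence of any exit contact.

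Other points also stand:

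- Interviews are one of three components. Attendance and adherence are recorded during the treatment visits, with no restriction to completers.
- Retention is itself a primary endpoint, so heavy drop-out would be reported beside the interviews. Section 6.1.1 also says that withdrawals associated with adverse events will be monitored.
- Leaving need not mean rejecting CATCH. Section 4.7.1 includes adverse events and hospitalisation for an exacerbation.
- The interview precedes the Week 10 evaluation, so someone lost between the two could be interviewed and still not be evaluable.
- Section 8 describes the 22 as randomised. Read literally, 15 interviews cover the arm. Attachment A places consent and eligibility checks at or before baseline, so some of the 40 could be lost before allocation.

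Against the last point, Section 4.6 attributes the fall from 40 to 22 to drop-outs, though it does not say when they occur or from which arm. None of these points supplies a rule for choosing interviewees, a contact for someone who stops during the six sessions, or a denominator for attendance and adherence.

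**Conclusion.** The point holds as a risk of bias in a primary endpoint, not as a demonstrated overstatement. The only component that records participants' views is planned in a number and at a time that suit those who remain, with no provision for those who stop.

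If all 40 are randomised, about 12 of about 27 CATCH participants go uninterviewed. Expected leavers are about 12 or about 9, depending on which evaluable figure is right and assuming equal loss by arm. All of these numbers fall if losses come before randomisation.

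The direction of any bias is probably towards stayers' views, but its size is unknown because it depends on what leavers think and why they left. It would be tempting to express it as a percentage finding CATCH acceptable. The qualitative analysis is thematic and defines no such percentage, so none is given here. The attendance and adherence figures above are illustrations on assumed values. They show only that the denominator must be fixed in advance.

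**What to change.** 1. In Section 3.1 and Attachment A, replace the fixed count of 15 with an offer of the phone interview to every participant randomised to CATCH, at Week 7 for those who continue and on stopping for those who do not. Report themes separately for stayers and leavers.
2. In Sections 3.2.1 and 6.1.1, define attendance (of 6 sessions) and home-practice adherence (of 6 × 7 = 42 days, against the 70% goal) over all participants randomised to CATCH, counting sessions and days after stopping as not done.
3. Reconcile 22 and 26 evaluable between Section 4.6 and the Protocol Summary, and state how many of the 40 enrolled are to be randomised.

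The cost is protocol wording and up to about 12 more short calls with the existing interview guide. Some leavers will decline, and reported attendance and adherence will be lower. The change needs to be in place before participants leave, because their views are hard to recover afterwards.
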